**13.3.1.6. Secondary Estimand (Hypothetical)**

The secondary estimand for the primary endpoint is defined as follows:

- Treatment difference in ICP measurement between Presendin and placebo at Week 24 for all patients who are randomised and start treatment, if all patients adhered to treatment, where patients did not have medications or procedures likely to materially affect ICP.

The secondary estimand for the initial secondary endpoint will be defined as:

- Treatment difference in PMD between Presendin and placebo over 24-weeks for all patients who are randomised and start treatment, if all patients adhered to treatment, where patients did not have medications or procedures likely to materially affect PMD.

All details will be defined in the SAP.

**13.3.2. Analysis Populations**

The following analysis populations are planned for this trial:

Study Number: INVEX-CLIN-IIH-301 Protocol	Compound No.: Presendin
	Version: 3.0

- **Safety Population:** The Safety population includes all patients randomised to treatment who receive at least one dose of trial medication. This will be the population used for all safety analyses unless otherwise specified.
- **Intent-To-Treat Population (ITT):** The ITT population includes all patients randomised to treatment. This will be the main population for all efficacy analyses unless otherwise specified.
- **Per Protocol (PP):** The PP population includes all patients randomised to treatment without important non-evaluable protocol deviations. Only protocol deviations with the potential to affect the trial results significantly, or to invalidate the interpretation of the data obtained, will lead to exclusion of patients from the PP population. Protocol deviations to be considered will include (but will not be limited to):
  - Failure to meet inclusion/exclusion criteria
  - Wrong treatment or incorrect volume of drug administration
  - Prohibited concomitant medications
  - Compliance of less than 75% or >125% with trial drug administration
  - Use of rescue procedures, including, off-protocol LPs, LP shunts or bariatric surgery

Assignment of patients to populations will be confirmed at a blinded data review meeting to be held before the trial database is locked.

If a patient is randomised incorrectly or is administered the incorrect trial medication, analyses of the ITT will be based on the assigned treatment, whereas all other analyses will be based on the actual treatment received.

### 13.3.3. Treatment Comparisons

Treatment comparisons will be undertaken between active and control groups. The primary outcome will be analysed as described in Section 13.2.1.

### 13.3.4. Safety Analyses

Safety will be evaluated from reported AEs, changes in clinical laboratory values, changes in vital signs, and ECG results.

All safety analyses will be performed on the Safety population.

Study Number: INVEX-CLIN-IIH-301 Protocol	Compound No.: Presendin
	Version: 3.0

#### **13.3.4.1. Adverse Events**

All AEs, TEAEs, and SAEs will be coded using the MedDRA dictionary (the most recent version before starting the trial will be used).

An AE is defined as treatment-emergent if the first onset or worsening is after the first administration of trial medication.

The number and percentage of patients reporting TEAEs, grouped by MedDRA system organ class and preferred term will be tabulated by treatment group. Summaries will be presented for all TEAEs, TEAEs by severity and TEAEs by relationship to trial medication.

In the AE data listings, all AEs will be displayed. Adverse events that are not treatment-emergent will be flagged. The observation period in which an AE started will also be provided.

Non-protocol LPs, interventions for IIH, hospital admission for IIH exacerbation will be displayed by trial arm. Treatment failures will be displayed by trial arm.

#### **13.3.4.2. Clinical Laboratory Evaluations**

Laboratory test results for each biochemistry and haematology parameter will be summarized descriptively by treatment group and time point as both observed values and change from baseline values.

The number of patients with clinical laboratory (biochemistry, haematology, and urinalysis) values categorized as below, within, or above the normal ranges (or as either normal or abnormal for urinalysis variables that do not have quantitative ranges), will be tabulated in relation to baseline (shift tables), for each clinical laboratory analyte by treatment group and time point.

Laboratory values will be displayed in the data listings and those that are outside the reference ranges will be flagged, along with corresponding normal ranges. Any patients with any markedly abnormal laboratory results will also be provided in a listing.

Pregnancy test results including reason, if not performed, will be listed.

#### **13.3.4.3. Vital Signs and Body Mass Index Evaluations**

Descriptive summaries of observed values and changes from baseline will be calculated for systolic blood pressure, diastolic blood pressure and heart rate by treatment group and time point.

Study Number: INVEX-CLIN-IIH-301 Protocol	Compound No.: Presendin
	Version: 3.0

Body mass index will be derived at Screening, Baseline and Weeks 4, 8, 16, 24, 32 and 48 using height captured at Screening and weight at the respective assessment. Body mass index and weight will be summarized descriptively by treatment group and time point as both observed values and change from baseline values for Safety and ITT populations.

#### **13.3.4.4. Electrocardiogram**

Descriptive statistics of observed values and change from baseline will be presented for ECG measures of PR interval, QRS interval, QT interval, QT interval corrected according to Fridericia's formula (QTcF). These summaries will be presented by treatment and time point for the Safety population.

The number and percentage of patients with values beyond clinically important limits will be summarised including those with an increase in QTcF >30 msec increase from baseline and >60 msec increase from baseline or those with an absolute QTcF value of >450 msec (male patients) or >470 msec (female patients).

#### **13.3.4.1. Other Safety Evaluations**

Non-protocol LPs, interventions for IIH, hospital admission for IIH exacerbation will be displayed by trial arm.

#### **13.3.5. Patient Reported Outcomes Analyses**

All patient reported outcome endpoints (VFQ-25, HIT-6, SF-36, EQ-5D-5L) will be analysed as observed and presented with change from baseline in a descriptive summary of treatment and visit

The number and percentages of PGIC responses will be tabulated by treatment and visit.

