### Quality of life in IHH

IHH has a detrimental effect on all aspects of the patient's quality of life; the majority of which is driven by headache [Kleinschmidt, 2000, Mulla, 2015; Daniels, 2007; Digre 2015]. IHH also impacts visual function with PMD correlating with quality of life [Bruce 2016]. Patient reported outcomes in clinical trials are essential not only to permit health technology assessments and cost effectiveness analysis, but also as key outcomes for a therapy's effectiveness [Deiner, 2019]. There is currently no IHH disease specific quality of life outcome measure.

Whilst there are differences in the choice of the tools used in the trials, they all commonly used the short-form 36 health survey (SF-36) [Mollan, 2021, Wall, 2014, Digre, 2015; Bruce, 2016; Ball, 2011]. The physical component score of the SF-36 has been shown to correlate significantly with changes in ICP [Grech 2021]. The EuroQol –5 dimension (EQ-5D-5L) [Euroqol, 1990] is typically employed for health technology assessments and cost effectiveness [Ottridge, 2017; Ball, 2011]. Using the EQ-5D-5L in isolation may lack sensitivity as compared to the SF-36 for IHH. The National Eye Institute Visual Function Questionnaire-25 and 10-item supplement [Mangione, 2001] has also been utilised to assess visual related quality of life in IHH and is associated with improvement in visual field [Bruce 2016; Mangione 1998; Raphael 2006]. The 10-Item neuro-ophthalmic supplement was found to be significantly discriminating in a previous IHH drug trial [Wall 2014].

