### **2.4. Exploratory Objectives**

To determine the effect of Presendin on:

- Macular ganglion cell layer/complex thickness
- Headache responder rate:  $\geq 30\%$  reduction in monthly headache days
- Headache responder rate:  $\geq 30\%$  reduction in moderate to severe monthly headache days
- Patient Reported Outcomes
- Body Mass Index
- Body Weight
- Health Utilisation

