### **6.1.2. Visit 2 Baseline**

- Review eligibility criteria
- Concomitant medications review
- Headache preventative medication review

Study Number: INVEX-CLIN-IIH-301 Protocol	Compound No.: Presendin
	Version: 3.0

- Review headache diary (Patient must meet required number of headache days as per inclusion criteria. If the headache diary exceeds 7 days, then eligibility will be based on the last 7 days of the screening period, i.e., the 7 days prior to randomisation visit)
- Vital signs (triplicate readings for blood pressure and heart rate will be taken at 1-minute intervals)
- Body weight and BMI
- Adverse events review
- Targeted physical examination
- Urine pregnancy test (for women of childbearing potential)
- Electrocardiogram
- Visual Assessments to both eyes
  - Frisén grading will be assessed by the site
  - Optical coherence tomography imaging
    - Sites should initially check the scan quality. The OCT scan should then go through the upload process to the OCT Reading Centre, without delay. The OCT scan will then be reviewed by the OCT Reading Centre for a full quality assessment. The report from the OCT Reading Centre will be sent to the site. Where the OCT is of insufficient quality it should be repeated as soon as possible at an unscheduled visit. Where the OCT processing is of insufficient quality it should be reprocessed as soon as possible by the site.
  - Humphrey Visual Field (24-2 SITA-Standard)
    - Sites should initially check the performance quality of the HVF (to ensure no more than 15% false positives). The HVF should then be uploaded to the Visual Field Reading Centre without delay (an initial quality assessment takes place during the upload procedure). The HVF will then be reviewed by the Visual Field Reading Centre for a full quality assessment. The report from the Visual Field Reading Centre will be received by the site. Where the visual field is of insufficient quality it should be repeated at an unscheduled visit without delay.
  - Visual Acuity (LogMAR score)
- Patient reported outcomes: VFQ-25 & 10-item supp, HIT-6, SF-36 and EQ-5D-5L in diary
- Health Utilisation Form
- Laboratory assessments

Study Number: INVEX-CLIN-IIH-301 Protocol	Compound No.: Presendin
	Version: 3.0

- Anti-Drug Antibodies (ADA) blood sampling
- Patient randomised
- Trial medication training

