### **13.2.2. Stratification**

At the outset, it is expected that markers of disease severity will be prognostic of potential efficacy. For this reason, it is proposed to stratify randomisation by, baseline ICP (<35cm or  $\geq 35$  cm), baseline body mass index (< 30 kg/m^2 or  $\geq 30$  kg/m^2) and baseline PMD (worse than or equal to -3.5dB or better than -3.5dB).

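### The exploratory PROs, body weight and BMI get by-arm descriptive tables only; a baseline-adjusted Week 24 difference with a 95% CI would serve the stated objective better at almost no cost

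*Protocol*

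**What the plan says.** All references are to protocol v3.0, the latest version whose statistical section is at hand.

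- **PROs, section 13.3.5.** VFQ-25, HIT-6, SF-36 and EQ-5D-5L "will be analysed as observed and presented with change from baseline in a descriptive summary of treatment and visit". PGIC responses are tabulated as counts and percentages.
- **Weight and BMI, section 13.3.4.3.** These "will be summarized descriptively by treatment group and time point as both observed values and change from baseline values", for the Safety and ITT populations.
- **Objective, section 2.4.** PROs, BMI and body weight stand in a list headed "To determine the effect of Presendin on". They are exploratory, here and in section 3.4.
- **Baseline data.** The Visit 2 procedures (section 6.1.2) include "Patient reported outcomes: VFQ-25 & 10-item supp, HIT-6, SF-36 and EQ-5D-5L in diary". Table 1 repeats these questionnaires at six later visits (Visits 5 to 10). Weight and BMI are also measured at Visit 2 and at Visits 5 to 10.
- **Stratification, section 13.2.2.** The protocol states "At the outset, it is expected that markers of disease severity will be prognostic of potential efficacy" and stratifies on baseline ICP, BMI and PMD.

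Neither 13.3.5 nor 13.3.4.3 names a between-arm estimate, a confidence interval, a baseline covariate or a stratification term. For ICP, by contrast, the sample size section specifies ANCOVA with baseline ICP and stratification terms.

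**The concern.** An aim of determining the effect of a drug calls for a between-arm difference with a measure of its uncertainty. A table of mean changes per arm and visit leaves readers to form that difference themselves. They will usually do so by subtracting mean changes.

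That contrast subtracts the whole baseline value, where regression adjustment subtracts only the part that predicts the outcome. It therefore carries more variance than the collected data require. It also makes no use of factors that the protocol itself expects to be prognostic. As-observed means at a visit describe only the patients with data at that visit, so differential drop-out could affect the comparison. The documents give no evidence that it will.

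What is at stake is modest: the usefulness of exploratory results. Still, the background section describes PROs in clinical trials as needed for health technology assessment, "but also as key outcomes for a therapy's effectiveness".

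**Working it through.** **No plan figure to reproduce.** The protocol gives no effect size, SD, correlation, power or sample size for any PRO, for weight or for BMI. What can be checked is how two ways of comparing the arms differ in variance.

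**Inputs.**
- ρ, the within-patient correlation between baseline and Week 24: not given for these endpoints, so it is an assumption and is varied from 0.3 to 0.95.
- The only within-patient correlation in the document is the serial correlation for PMD (Perimetric Mean Deviation Power, section 13.2.1.1): 0.4 expected, 0.3 as the low case. It belongs to a different outcome and serves only as a reference point.
- SD: assumed equal at baseline and Week 24, and set to 1.

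**Formulas, per-patient variance entering the arm difference.**
- Change score: 2(1 − ρ).
- Baseline-adjusted: 1 − ρ² = (1 − ρ)(1 + ρ).
- Ratio, adjusted to change score: (1 + ρ)/2. Variance saved: (1 − ρ)/2.
- CI width saved: 1 − √((1 + ρ)/2).

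**Results.**

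| Assumed ρ | Change score | Adjusted | Variance saved | CI width saved |
|---|---|---|---|---|
| 0.3 | 1.40 | 0.91 | 35% | 19.4% |
| 0.4 | 1.20 | 0.84 | 30% | 16.3% |
| 0.5 | 1.00 | 0.75 | 25% | 13.4% |
| 0.7 | 0.60 | 0.51 | 15% | 7.8% |
| 0.9 | 0.20 | 0.19 | 5% | 2.5% |
| 0.95 | 0.10 | 0.0975 | 2.5% | 1.3% |

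**Check against observed values.** Section 13.3.4.3 also tabulates observed values, and 13.3.5 can be read the same way, so a reader could compare Week 24 means instead. That contrast has variance 1, and adjustment saves ρ² of it: 9% at ρ = 0.3, 16% at 0.4, 25% at 0.5, 49% at 0.7 and 81% at 0.9. The change score is the noisier of the two unadjusted contrasts below ρ = 0.5, and the observed score is the noisier above it. For any ρ strictly between 0 and 1 the adjusted contrast has the smallest variance of the three, so there is no need to know ρ in advance to choose it.

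**Scope.** Any gain from the stratification factors beyond the baseline value is not quantified here. PGIC has no baseline score, so the calculation does not apply to it.

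**The case against.** **The endpoints are exploratory.** No hypothesis, estimand or sample size depends on them, and descriptive reporting of exploratory endpoints is conventional. The aim is worded as a common stem for a whole list, and the background remark concerns PROs in trials generally. This stands. It makes the point an improvement and not the correction of an error.

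**The size is assumed.** A reader might infer that the plan loses 15 to 35% of its precision. The documents do not support that. The range is a variance saving, it rests on an assumed ρ of 0.3 to 0.7, and it compares a contrast that a reader would form with one that the protocol does not plan. It should not be carried over to weight and BMI, which may track far more closely. For the same reason, power figures would be out of place: no test of these endpoints is planned.

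**The tables are not worthless.** A reader might also infer that the objectives go unanswered, or that the comparison is biased. Neither follows. By-arm summaries allow a rough unadjusted difference, and randomisation makes that unbiased with complete data. Drop-out bias is only a possibility: section 11.2.1 encourages patients who stop treatment to attend all visits up to Visit 10.

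**The SAP may cover it.** Section 13 leaves detailed methods to the SAP, and section 13.3.6 refers to it for endpoint-specific imputation. Nothing in the protocol forbids an added model. But 13.3.5 does not leave the choice open: it fixes an as-observed, descriptive presentation. An SAP that only elaborates that sentence would still produce no estimate.

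**The version.** The file includes v4.0 appendices without a v4.0 statistical section, so the v4.0 wording cannot be confirmed. The point applies to the v3.0 text.

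**Conclusion.** The point holds as a minor, inexpensive improvement. Protocol v3.0 specifies descriptive by-arm summaries for the exploratory PROs, weight and BMI. It therefore plans no effect estimate or interval for endpoints on which it aims to determine an effect, although it collects everything needed to produce one.

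A change-score comparison read from the tables has more variance than a baseline-adjusted one. With equal SDs the saving is (1 − ρ)/2: 15 to 35% of variance, or about 8 to 19% of CI width, for assumed ρ between 0.7 and 0.3. It is 5% of variance or less if weight or BMI tracks at 0.9 or above, and there the missing estimate and interval matter more than the efficiency. All these figures rest on assumed correlations. The primary and secondary analyses, the type I error rate and the sample size are unaffected.

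**What to change.** Keep the descriptive tables. Add to section 13.3.5, or to the SAP, a sentence to this effect:

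> For VFQ-25 (with supplement), HIT-6, SF-36 and EQ-5D-5L, the Presendin minus placebo difference at Week 24 with 95% CI will be estimated in the ITT population from a longitudinal mixed model with treatment, visit, treatment-by-visit interaction, continuous baseline score and the three stratification factors (baseline ICP, BMI and PMD).

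Add the same for body weight and BMI in section 13.3.4.3, with the continuous baseline value as covariate. For BMI, the continuous baseline replaces its stratum. Label all these analyses exploratory, with no multiplicity claim. Leave PGIC as a tabulation.

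The cost is two sentences and a few model runs on data already collected: no new data, visits or alpha. The one drawback is a longer list of exploratory estimates to report and label as such. The sentences should be in place before unblinding, since a model added afterwards would be post hoc.

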#### **13.3.6. Missing Data**

Although every effort will be made to collect responses from all patients at all scheduled time points, there undoubtedly will be some missing data. The SAP describes in detail steps for dealing with missing data using relevant imputation strategies for specific endpoints that adjust for treatment arm, centre, baseline value, and stratification variables.

#### **13.3.7. Reporting Deviations from the Statistical Plan**

Any deviations from the planned analyses will be described and justified in the final clinical trial report.

Study Number: INVEX-CLIN-IIH-301 Protocol	Compound No.: Presendin
	Version: 3.0

## 14. TRIAL ADMINISTRATION

### 14.1. Regulatory and Ethical Considerations, Including the Informed Consent Process

Before initiation of a trial site, the Sponsor will obtain approval from the appropriate regulatory agency to conduct the trial in accordance with ICH-GCP and applicable country-specific regulatory requirements.

The trial will be conducted in accordance with all applicable regulatory requirements.

The trial will be conducted in accordance with the EU Clinical Trial Regulation 536/2014, ICH-GCP, all applicable patient privacy requirements and the ethical principles that are outlined in the Declaration of Helsinki 2013, including, but not limited to:

- An IEC/Institutional Review Board review and approval of trial protocol and any subsequent amendments and all ICFs or other information given to the patient
- Patient informed consent
- Investigator reporting requirements

The Sponsor will provide full details of the above procedures, either verbally, in writing, or both.

Written informed consent must be obtained from each patient before participation in the trial. Written informed consent will be collected following a review of the patient's information leaflet by the potential patient and a discussion between the patient and the Investigator or suitably qualified designee.

The Investigator will cooperate with all regulatory inspections and will notify the Sponsor as soon as they are aware of an inspection which may involve this trial. With the exception of statutory regulatory authority inspections, the Sponsor will be consulted in the event of inspection of the clinical site(s) by an outside authority before the Inspectors are permitted access to any of the trial records or the trial areas.

### 14.2. Trial Monitoring

In accordance with applicable regulations, ICH-GCP, the monitoring plan and the Sponsor's and/or delegate procedures, monitors will contact the site before the start of the trial to review with the site staff the protocol, trial requirements, and their responsibilities to satisfy regulatory, ethical, and the Sponsor's requirements. When reviewing data

Study Number: INVEX-CLIN-IIH-301 Protocol	Compound No.: Presendin
	Version: 3.0

collection procedures, the discussion will include identification, agreement and documentation of data items for which the eCRF will serve as the source document.

The Sponsor and or delegated monitors will perform risk-based monitoring during the conduct of the trial to ensure that:

- The data are authentic, accurate and complete
- The patient's safety and rights are being protected
- The trial is conducted in accordance with the currently approved protocol and any other trial agreements, ICH-GCP and all applicable regulatory requirements

#### **14.2.1. Access to Source Data**

The Investigator and the head of the medical institution (where applicable) agrees to allow the monitor, Sponsor-appointed auditors and regulatory inspectors direct access to all relevant documents.

#### **14.2.2. Data Handling and Record Keeping**

Following closure of the trial, the Investigator or head of the medical institution (where applicable) must maintain all site trial records (except for those required by local regulations to be maintained elsewhere) in a safe and secure location. The records must be easily accessible when needed (e.g., for a Sponsor audit or regulatory inspection) and must be available for review in conjunction with assessment of the facility, supporting systems, and relevant site staff.

Where permitted by local laws/regulations or institutional policy, some or all of the records may be maintained in a format other than hard copy (e.g., microfiche, scanned, electronic); however, caution must be exercised before such action is taken. The Investigator must ensure that all reproductions are legible and are a true and accurate copy of the original. In addition, they must meet accessibility and retrieval standards, including regeneration of a hard copy, if required. The Investigator must also ensure that an acceptable back-up of the reproductions exists and that there is an acceptable quality control procedure in place for creating the reproductions.

The Sponsor will inform the Investigator of the time period for retaining the site records in order to comply with all applicable regulatory requirements. The minimum retention time will meet the strictest standard applicable to a particular site, as dictated by local laws/regulations, the Sponsor SOPs and/or institutional requirements.

The Investigator must notify the Sponsor of any changes in the archival arrangements, including, but not limited to archival of records at an off-site facility or transfer of

Study Number: INVEX-CLIN-IIH-301 Protocol	Compound No.: Presendin
	Version: 3.0

ownership of the records in the event that the Investigator is no longer associated with the site.

